### **Compliance and Missing Data**

#### **Compliance/Adherence**

Compliance with study procedures is defined as the patient making a good faith effort to complete all protocol-related assessments. If a subject is not compliant, the treating investigator should assess barriers to compliance. Patients whose actions cause 2 or more deviations despite efforts to improve non-compliance may be removed from the study.

Compliance with oral medication is defined as the patient taking  $\geq 75\%$  of the prescribed doses/days within a treatment cycle. The desired level of compliance is  $> 75\%$ . Patients who cannot maintain this level of compliance may be removed from the study. Patients

who consistently cause deviations despite efforts to improve non-compliance may be removed from the study. See monitoring compliance with oral medication.

Subjects who leave the study for non-compliance will not be followed-up.

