### **1.3.5 Active phase, combination treatment**

After Week 2, regular study visits will occur in the outpatient clinic at an interval of 14 or 21 days (depending on whether treatment includes nivolumab or pembrolizumab) as per the Study Calendar.

Subjects will receive treatment up to 109 weeks. Subjects may elect to discontinue therapy at any time for any reason. Subjects will remain on the active treatment phase of the study until confirmed disease progression, unacceptable toxicity, or withdrawal of consent, up to a maximum treatment duration of 109 weeks. Once the subject discontinues active treatment, the subject will enter the follow-up phase.

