#### **1.7.11 TOXICITY MONITORING AND ADVERSE EVENT REPORTING**

All patients who receive one dose of protocol therapy will be evaluable for assessment of toxicity. Prior to each cycle the treating physician will fully assess the patient's condition with respect to possible treatment related toxicities. All adverse events, whether observed by the physician or reported by the patient, occurring during the active portion of therapy, or up to 30 days after the last dose of treatment will be graded by a numerical score according to the NCI's Common Terminology Criteria for Adverse Events (CTCAE), Version 4.0

(<http://ctep.cancer.gov/reporting/ctc.html>) and recorded in the patient's medical record. For the purposes of reporting laboratory abnormalities, only Grade 3-4 adverse events will be recorded on the adverse event CRF pages. Grade 1-2 laboratory abnormalities will not be recorded on the adverse event CRF pages, unless the investigator judges it to be clinically significant and wishes to report it. Information entered on the adverse event CRF pages will include:

- Specific type and duration of reaction (i.e., start and stop dates, resolution).
- Severity/grade.
- Relationship to study drug (causality, attribution).
- Management of the event, if treated with medication and other actions taken to alleviate the clinical event.
- Whether or not it was considered a SAE.

A preexisting condition is one that is present at the start of the study. A preexisting condition will be recorded as an adverse event if the frequency, intensity, or the character of the condition worsens during the study period.

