### **SAE Reporting Period**

The SAE reporting period starts at start of treatment and lasts through 30 days after the patient's last dose or start of subsequent therapy, whichever comes sooner. SAE's that during screening period prior to the start of therapy are presumed to be unrelated to the study and need not be reported as SAEs.

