### **SAE Reporting Timeline**

All "unexpected" (defined below) and/or "serious" (defined below) adverse events related to pembrolizumab/nivolumab or the combination of pembrolizumab/nivolumab + trigriluzole and occurring during the active portion of therapy, or up to 30 days after the last dose of treatment, will be reported to the Office of Human Research Services at [contact] or [contact]. Events will be promptly reported, in writing, to the local IRB in accordance with IRB policy. If a death occurs the IRB will be notified **within 24-hours** of initial receipt of information. All other SAEs must be reported to the IRB **within 3 to 10 days** of initial receipt of information. Written follow-up reports are required when additional information is needed to fully characterize the event. Copies of each report sent to the IRB will be kept in the study regulatory file.

Collaborating institutions will report all SAEs to RCINJ Office of Human Research Services (OHRs) and RCINJ OHRs will be responsible for forwarding SAE reports to the IRB, FDA, Fox Chase Chemical Diversity Center, Inc. and Biohaven Pharmaceuticals.

In addition to reporting to the local IRB, reporting to external bodies such as industry and/or the FDA may be necessary.

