 **RUTGERS | eIRB**  
APPROVED  
Form Version v120116

IRB ID: Pro20170000453  
Approval Date: 10/4/2019  
Expiration Date: 4/3/2020

	Off treatment but on study Q6 weeks	Off treatment but on study Q12 weeks	Safety Follow-up (12 weeks after last dose of rx)	Long-Term Follow-up Q12 weeks
Scheduling Window (Days):	±14	±14	±28	± 28
Prior and Concomitant Medication Review	X	X	X	
Assess Baseline Symptoms/Adverse Events and Compliance	X	X	X	
Vital Signs and Weight, ECOG Performance Status, Physical Examination	X	X	X	
Routine Safety Laboratory Studies	X	X	X	
Tumor Assessment 		X	X	
Post-study survival status, and receipt of subsequent anticancer therapy				X

Footnotes

1. If a subject has discontinued active treatment due to reasons other than PD (such as toxicity or patient preference), the subject will continue to have CT scans and follow-up visits to monitor them until Week 49.
2. Tumor Assessment must be performed at the same Weeks as subjects who remain on active treatment (Week 7, Week 13, and then Q12 weeks up until Week 49).
3. Safety follow-up visit will occur at Week 61 for subjects who complete all treatment (Week 49), but it will occur prior to Week 61 if active treatment is discontinued early for PD or other reasons.
4. Long-term Follow-up. Subjects will remain in the follow up phase of the trial for up to 3 years until the start of another therapy, withdrawal of consent or death.

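### The rule of no follow-up after leaving for non-compliance is inconsistent with the 12-week safety visit and the end-of-follow-up rule, and weakens ascertainment in the 30-day adverse event window

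*Combined protocol and SAP*

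**What the plan says.** The Compliance/Adherence text in Section 6.1 ends with this rule: "Subjects who leave the study for non-compliance will not be followed-up". Two routes to removal come before it, and both are optional. One is oral compliance below 75% of prescribed doses or days in a cycle (also in Section 1.7.10). The other is repeated deviations: "Patients whose actions cause 2 or more deviations despite efforts to improve non-compliance may be removed from the study". Section 1.7.13, item f, lists non-compliance, at the investigator's discretion, among the criteria for ending treatment.

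Other sections set the safety and survival follow-up:

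- Section 1.7.11, opening text: adverse events "occurring during the active portion of therapy, or up to 30 days after the last dose of treatment will be graded".
- Section 1.7.11, SAE Reporting Period: the window runs to 30 days after the "last dose or start of subsequent therapy, whichever comes sooner".
- Section 1.7.11, SAE Reporting Timeline: related serious or unexpected events "occurring during the active portion of therapy, or up to 30 days after the last dose of treatment, will be reported".
- Section 1.10, follow-up calendar: one column is headed "Safety Follow-up (12 weeks after last dose of rx", with a window of ±28 days. Footnote 3 says of this visit that "it will occur prior to Week 61 if active treatment is discontinued early for PD or other reasons".
- Section 1.3.5: "Once the subject discontinues active treatment, the subject will enter the follow-up phase".
- Section 1.3.7: follow-up lasts up to three years and ends earlier only for another therapy, withdrawal of consent or death.

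**The concern.** The rule in Section 6.1 has no time limit and no exception for safety. It applies to people who have been dosed and who may still be willing to be followed, because removal is a decision of the investigator.

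The subjects concerned may not be a random subset. Low pill-taking can be a consequence of poor tolerability: Section 1.7.7 itself gives mild dizziness that a patient cannot tolerate as an example of a reason to lower the trigriluzole dose. A subject removed for missed capsules may also have received a PD-1 antibody, and the same section warns that immune-related events can appear months after the last dose. Dropping such subjects from follow-up could make the combination look better tolerated than it is, in a trial whose primary objective is safety. Survival status, which feeds overall survival and the 1- and 2-year landmark rates, would stop as well.

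**Working it through.** No sample size or error rate is involved, so the check is a comparison of the rules plus simple date arithmetic.

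**Does any provision exempt non-compliance?**

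| Provision | When it ends or applies | Exception for non-compliance |
|---|---|---|
| AE collection (1.7.11) | 30 days after last dose | None |
| SAE reporting (1.7.11) | 30 days after last dose, or start of subsequent therapy if sooner | None |
| Safety visit (1.10, footnote 3) | 12 weeks after last dose, including early stops for progression or any other reason | None |
| Long-term follow-up (1.3.7) | 3 years, another therapy, withdrawal of consent, death | None |

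Exceptions found: 0. Since Section 1.7.13 names non-compliance as a ground for stopping, it falls within the other reasons in footnote 3. Since removal is not withdrawal of consent, it meets none of the ending conditions in Section 1.3.7.

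**What a literal reading removes, per subject**

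1. Active AE/SAE ascertainment for 30 days after the last dose. The follow-up calendar has no visit fixed at day 30. The visit it keys to the last dose is the 12-week one.
2. The safety visit. 12 × 7 = 84 days; 84 − 28 = 56 and 84 + 28 = 112, so it falls on day 56 to 112. Relative to the close of the 30-day window, that is 56 − 30 = 26 to 112 − 30 = 82 days later. It includes an adverse event review, examination, safety laboratory tests and a tumor assessment.
3. Survival contacts. 3 years × 52 = 156 weeks; 156 / 12 = 13. This is a ceiling, because death or another therapy ends follow-up earlier.

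**How many subjects?** The documents give no expected number of removals for non-compliance, so no total effect can be calculated.

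**The case against.** The best defence is that Section 6.1 sets a specific rule for subjects who leave the study, while the other provisions are general rules for subjects who stop treatment. The protocol does distinguish the two states: the calendar has columns for subjects off treatment but still on study, and Section 1.3.6 contrasts remote contact with removing a patient altogether. On this view Section 1.3.5, Section 1.3.6 and those columns are general rules with one exception, and I do not count them as contradictions. Footnote 3 is also imperfect support, since it treats Week 49 as the end of treatment while Sections 1.3.2 and 1.3.5 allow 109 weeks.

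This does not dispose of the point. Footnote 3 explicitly covers every reason for an early stop, and Section 1.3.7 gives a list of endings that omits non-compliance. Section 1.7.13 puts removal from study and the end of treatment under one heading, so staff cannot tell which state a non-compliant subject is in. If the word follow-up in Section 6.1 is taken to mean long-term follow-up only, the sentence still conflicts with Section 1.3.7.

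Three further defences have some force. Removal is discretionary, and re-education and attention to barriers are expected for a non-compliant subject. Some of these subjects will be unwilling to attend. An investigator could stop the drug and keep the subject on study. These reduce how often the problem arises, but they do not settle which rule governs when it does. Section 1.3.7 also accepts medical records and a death index, so survival status need not depend on the subject's cooperation.

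A reader might infer that the sentence cancels AE/SAE reporting. It does not say so: an event that comes to light within the reporting window remains reportable. What suffers is the active search for events.

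**Conclusion.** The concern holds. The Section 6.1 sentence is inconsistent with the 12-week safety visit and with the end-of-follow-up rule in Section 1.3.7, and it undercuts active ascertainment in the 30-day AE/SAE window. It should be corrected.

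The size is known only per removed subject, as set out above. That the loss may be informative rests on the assumption that some poor pill-taking is caused by toxicity, which is plausible from Section 1.7.7 but is not measured anywhere in the documents. The survival endpoints affected are secondary and descriptive.

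A reader might go further and infer that the rule biases the maximum tolerated dose. The documents do not support that. The Missing data text in Section 6.1 already replaces subjects who are not evaluable for the whole dose-limiting toxicity period, and nothing indicates how many removals would fall inside that period.

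**What to change.** Replace the Section 6.1 sentence with:

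> Subjects removed for non-compliance stop study treatment but, unless they withdraw consent, remain under AE/SAE collection through 30 days after last dose (for SAEs, or until subsequent therapy starts, if sooner), have the 12-week safety visit (or remote contact as in Section 1.3.6), and continue survival contact as in Section 1.3.7.

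Also record, at the time of removal, whether doses were missed because of an adverse event. That item is what would show whether these removals are related to tolerability.

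The cost is one replaced sentence and one recorded item. The safety visit, remote contact and survival contact already exist in the protocol. The downside is that some of these subjects will be hard to reach, so follow-up will be incomplete for them. No change to the counting of dose-limiting toxicities or to the replacement rule is needed for this point.

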### **Missing data**

Subjects who do not start study treatment or are not evaluable for toxicity for the entire DLT observation period will be replaced (up to 5 replacements).

### **Interim Analysis**

An interim analysis of safety data in the first 9 - 12 subjects may be reported at academic conference(s).

## **6.2 Data Collections and Records to be Kept**

### **Case Report Forms**

Completion of the electronic CRFs (eCRFs) will be done in accordance with the instructions in a study specific data capture plan. The electronic CRF stored in Oncore® will be the primary data collection document for the study. All eCRFs will be completed by clinical research coordinators of the Office of Human Research Services (OHRS) at the Cancer Institute of New Jersey. The eCRFs will be maintained in a confidential format in a secure database. The CRFs will be updated in a timely manner following acquisition of new source data. Only the key personnel delegated on the delegation of authority log are permitted to make entries, changes, or corrections in the CRF. All users of this system will complete user training, as required or appropriate per regulations. An audit trail will be maintained automatically by the electronic CRF management system.

### **Data Submission Timeline and Forms**

Completion of eCRFs will occur in accordance with NCI guidelines. Baseline (pre-study) eCRFs (e.g., enrollment, medical history, concomitant medications, disease assessment, etc.) will be completed no later than 14 days after the start of treatment. Treatment eCRFs (e.g., drug administration, adverse events, chemistries, etc.) will be completed no later than 14 days following each cycle of treatment. Off-treatment information (e.g., follow-up, best response, etc.) will be completed no later than 14 days after the end of protocol treatment.

## Research Charts

A research chart (i.e., shadow chart) is maintained at OHRS for each patient enrolled. Copies of significant study source documents will be maintained in the research chart. Examples of source document copies that will be maintained in the research chart include: signed informed consent form, documents that verify eligibility and treatment and documents that verify Grade 3-4 adverse events and response. This information will be updated on a prospective basis and will be confidentially maintained at the Cancer Institute of New Jersey, OHRS.

## Reports

The RCINJ PI is the sponsor-investigator of the IND (IND#133666) and RCINJ will be responsible for episodic and annual reporting to the FDA. Publications for submission and annual reports for the IRB will be written by the RCINJ PI and OHRS using the data captured on the e-CRFs.

### 6.3 Data and Safety Monitoring Plan

Monitoring of this study will occur in accordance with the NCI approved Data and Safety Monitoring Plan (DSMP) of RCINJ. The study team reviews all toxicity during the dose-escalation phase of studies and presents this data to the weekly Phase I meetings. The RCINJ Human Research Oversight Committee (HROC) is responsible for annual data and safety monitoring of phase I and phase II, therapeutic interventional studies that do not have an independent Data Safety Monitoring Board (DSMB). The primary focus of the HROC is review of safety data, toxicities and new information that may affect subject safety or efficacy. Annual safety reviews includes but may not be limited to review of safety data, enrollment status, stopping rules if applicable, accrual, toxicities, reference literature, and interim analyses as provided by the sponsor-investigator. The HROC in concert with the Quality Assurance Monitoring Team oversees the conduct of RCINJ cancer-related, sponsor-investigator therapeutic intervention and prevention intervention studies that do not have an external monitoring plan, ensuring subject safety and that the protocol is conducted, recorded and reported in accordance with the protocol, standing operating procedures (SOPs), Good Clinical Practice (GCP), and applicable regulatory requirements. All study staff must complete training and maintaining active certification in the use of human subjects in research.

### **Periodic Data Evaluation**

HROC meets approximately twice a month and each disease group is reviewed at least every 3 months. HROC will review all Dose Administration Memos (DAM) and dose-limiting toxicities (DLTs) for Phase I dose-escalation trials. Protocol suspensions and re-opening of accrual to the next cohort based on DLT evaluation, fall under the purview of the HROC.

An "initiation audit" will be conducted at the RCINJ in accordance with the DSMP following enrollment of the first two (2) or three (3) patients. Subsequent audits will occur on an annual basis prior to annual IRB continuing review, if the findings from the initiation audit were satisfactory. More frequent audits of patient data and study conduct will occur if necessary. Prior audit findings and/or situations that may arise during the course of the study will determine the need for more frequent auditing. All audit findings will be discussed with the principal investigator and reported to the RCINJ HROC and the Rutgers University IRB.

### **Type of Data Evaluated**

HROC monitors accrual, deviations, and SAEs.

### **Collection of Safety Information**

Safety information is collected and tallied in reports using OnCore.

### **Frequency Of Data Collection**

Data is collected at each study visit and follow-up contact. Safety data collection (including SAEs) starts after the first study treatment.

### **Reviewer of Data**

The members of OHRS management staff review the data for completeness. HROC monitors accrual, deviations, and SAEs. The PI will review data as needed for accuracy and consistency.

### **Schedule Of Review Of Cumulative Data**

There will be one planned interim analysis after 9-12 subjects are enrolled.

### **Tests for Safety Data**

N/A

### **Suspension of Research**

Protocol Number: RCINJ# 051707

PI Name: [name]

Protocol Title: A Phase I Study to Evaluate the Safety of Trigriluzole (FC-4157/BHV-4157) in Combination with PD-1 Blocking Antibodies

73

RESERVED FOR IRB STAMP  
DO NOT MODIFY THIS SPACE

Form Version v120116

IRB ID: Pro20170000453  
Approval Date: 10/4/2019  
Expiration Date: 4/3/2020

**RUTGERS | eIRB**  
**APPROVED**

If the combination is found to not be tolerable (MTD reached at lowest dosing cohort), accrual will halt until further review/amendment.

## **6.4 Reporting Results**

### **Sharing of Results with Subjects**

Individual subject results of routine diagnostic clinical tests and incidental findings will be shared with subjects at their office visits or by telephone by appropriate study staff (clinicians).

#### **Individual Results**

Individual subject results of routine diagnostic clinical tests and incidental findings will be shared with subjects at their office visits or by telephone by appropriate study staff (clinicians).

#### **Aggregate Results**

N/A

#### **Professional Reporting**

The policies and procedures of Rutgers University's legal department (see: Investigator's Brochure) will govern publication of the trial. It is expected that the results of this trial will be submitted for publication in a timely manner following the conclusion. The RCINJ PI, and all co-authors prior to submission or use, must review any abstract or manuscript.

#### **ClinicalTrials.Gov Registration And Data Reporting**

This study is registered at [clinicaltrials.gov](https://clinicaltrials.gov).

## **7.0 Data and/or Specimen Banking**

N/A

## **8.0 Other Approvals/Authorizations**

N/A

Protocol Number: RCINJ# 051707  
PI Name: [name]  
Protocol Title: A Phase I Study to Evaluate the Safety of Trigriluzole (FC-4157/BHV-4157) in Combination with PD-1 Blocking Antibodies

74

RESERVED FOR IRB STAMP  
DO NOT MODIFY THIS SPACE

**Appendix A: Performance Status Criteria**

ECOG Performance Status Scale		Karnofsky Performance Scale	
Grade	Descriptions	Percent	Description
0	Normal activity. Fully active, able to carry on all pre-disease performance without restriction.	100	Normal, no complaints, no evidence of disease.
		90	Able to carry on normal activity; minor signs or symptoms of disease.
1	Symptoms, but ambulatory. Restricted in physically strenuous activity, but ambulatory and able to carry out work of a light or sedentary nature (e.g., light housework, office work).	80	Normal activity with effort; some signs or symptoms of disease.
		70	Cares for self, unable to carry on normal activity or to do active work.
2	In bed <50% of the time. Ambulatory and capable of all self-care, but unable to carry out any work activities. Up and about more than 50% of waking hours.	60	Requires occasional assistance, but is able to care for most of his/her needs.
		50	Requires considerable assistance and frequent medical care.
3	In bed >50% of the time. Capable of only limited self-care, confined to bed or chair more than 50% of waking hours.	40	Disabled, requires special care and assistance.
		30	Severely disabled, hospitalization indicated. Death not imminent.
4	100% bedridden. Completely disabled. Cannot carry on any self-care. Totally confined to bed or chair.	20	Very sick, hospitalization indicated. Death not imminent.
		10	Moribund, fatal processes progressing rapidly.
5	Dead.	0	Dead.

Protocol Number: RCINJ# 051707

PI Name: [name]

Protocol Title: A Phase I Study to Evaluate the Safety of Trigriluzole (FC-4157/BHV-4157) in Combination with PD-1 Blocking Antibodies

79

RESERVED FOR IRB STAMP  
DO NOT MODIFY THIS SPACE

Form Version v120116

